6 DATA COLLECTION

All data will be entered by site personnel into an electronic data capture (EDC) system, (ArisGlobal) which will utilize eCRFs. The Investigator at the site will be expected to review

and approve eCRFs. All data will be subject to source document review by the Sponsor's (CryoLife) personnel or its representatives. Any corrections made to the eCRFs will be done so by a designated study coordinator or Investigator.

The eCRFs and patient's corresponding medical records (source documents) are to be fully available for review by the Sponsor's representatives at the scheduled site visits. These reviews verify adherence to the study protocol and data accuracy in accordance with federal regulations. All related electronic records at this site are subject to inspection by the Sponsor, its agents, and regulating authorities.

In accordance with ICH E6, Section 6.10, source documents include, but are not limited to the following:

- Clinic, office, hospital charts;
- Copies or transcribed health care provider notes which have been certified for accuracy after production;
- Recorded data from automated instruments such as Interactive Voice-response Systems, x-rays, and other imaging reports, e.g., Duplex Ultrasound (DUS), sonograms, CT scans, magnetic resonance images, and radioactive images (regardless of how these images are stored, including microfiche and photographic negatives);
- Correspondence regarding a study patient memorandum sent to IRB(s).

6.1 Study Endpoints & Variables

In the case of CEAs, the primary endpoint of the study will be rate of ipsilateral central neurologic events.

- Ipsilateral central neurologic events: Transient ischemic attack, amaurosis fugax, stroke, and symptomatic carotid occlusion.

In the case of all other (non-CEA) vascular procedures, the primary endpoint of the study will be primary patency in the target artery or vein.

- Primary patency (of target vessel): Loss of patency will be determined by the loss of previously palpable pulses, patients presenting with recurrent symptoms, a drop in ABI >0.15 in the case of lower limb artery repair, Doppler ultrasound findings of occlusion, angiography of the affected vessel or a combination of these.

The secondary endpoints of the study will include: overall survival rate, all-cause reoperation rate, device-related reoperation rate, explant rate, restenosis rate, adverse event rate, and secondary patency (HAR only).

- Overall Survival:
 - Early mortality: Death < 30 days following PhotoFix implantation.
 - Late mortality: Death ≥ 30 days following PhotoFix implantation, until last day of follow-up.
- All-Cause Reoperation Rate: The total number of reoperations required in patients over the follow-up period, which include the repair or alteration of the surgical area around the patch.

- **Device-Related Reoperation Rate:** The total number of unplanned reoperations required in patients over the follow-up period, which are determined by the surgeon to be device-related.
- **Explant Rate:** The total number of device explants over the course of follow-up. Explants will include the removal of PhotoFix for any reason after implantation.
- **Restenosis Rate:** The total number of documented cases of stenosis documented as the recurrence of abnormal narrowing of a vessel after corrective surgery.
- **Adverse Event Rate:** The total number of any unfavorable and unintended sign (including an abnormal laboratory finding), symptom, or disease temporarily associated with the use of a device, whether or not related to the device.
- **Secondary Patency (HAR only):** The time from implantation to the point where the access is abandoned.

Statistical analysis will be used to assess all study endpoints as applicable.

6.2 Records and Reporting

The Investigator must maintain adequate records for the study including, without limitation, access to original source documents, medical records, laboratory reports, signed informed consent forms, adverse event reporting to the Sponsor, information regarding patients who no longer choose to be in the study or were withdrawn, all correspondence with the IRB and/or Privacy Board and CryoLife, and other pertinent data.

Data will be collected within eCRFs designed specifically for this study.

6.3 Electronic Case Report Forms

The clinical data collected for the study will be obtained from patient records, source documents, and existing databases and reported to the sponsor via eCRFs, within the electronic database. Data variables to be obtained are outlined in Appendix D and are organized by eCRF. All data collected must be supported by source documents. Patient medical records, hospital charts, operative reports, laboratory and diagnostic testing results, office visits, and other relevant documents are to be utilized for collection of relevant data. The general time points for data collection include pre-operative screening, during/ immediately following the operation, and post-operative follow-up visits (Table 2). The electronic database will store all data within the following eCRFs: Informed Consent, Eligibility Evaluation, Baseline Assessments (Demographics, Medical History, Surgical History, and Social History), Imaging Evaluation, Medication, Operative Assessment, Follow-Up Evaluation, Adverse Event, Explant Evaluation, and End of Study.

6.4 Data Reporting

All data will be entered by site personnel into eCRFs. The Investigator at the site will be expected to review and approve eCRFs. Any corrections made to the forms at a study site will be done so by a designated study coordinator (or Investigator). Form changes will be tracked in the EDC.

6.5 Data Review

The completed eCRFs will be reviewed for completeness and clarity by the Sponsor's data manager and the Sponsor's representative clinical research associates. Throughout the study, the data manager and clinical research associates will issue queries for any information inadvertently omitted, inconsistent, not supported by source documents, or not answered within the EDC. The data manager may request further documentation when data issues, complications, device malfunctions, or explants are observed and reported. The site will be responsible for clarification and resolution of all queries. The data manager will close queries after sufficient clarification and resolution is achieved.

6.6 Data Quality Control

Site investigators will sign off on all study forms prior to data lock. Additionally, data will be 100% source document verified by the Sponsor or a representative of the Sponsor, as deemed necessary.

6.7 Statistical Analysis Plan

Enrolled patients will be described in aggregate and by indication (as deemed appropriate); baseline characteristics will include, but not limited to, age, sex, race, ethnicity, body mass index (BMI), comorbidities, fundamental diagnosis/etiology, and pertinent surgical history. Operative details will be described in aggregate and include a summary of the types of procedures performed, by relevant category. Parameters with continuous data types will be summarized using descriptive statistics, i.e., mean, standard deviation, and range. Categorical clinical parameters will be summarized based on percentages.

Ipsilateral central neurologic event rate, overall survival, re-operation rate, explant rate, and restenosis rate ($\geq 50\%$ stenosis) will be summarized based on percentages of affected patients and included in a table, which will summarize the endpoints in aggregate and by surgical indication (ex. CAS, ESRD, PAD, AAA, etc.). The summary of ipsilateral central neurologic event rates will include all events (transient ischemic attack, amaurosis fugax, stroke, and symptomatic carotid occlusion), as well as the incidence of each event individually.

Additional analysis of follow-up data will also be performed with the Kaplan-Meier method, as deemed appropriate by the incidence of events. Kaplan-Meier plots may be generated for endpoints including overall survival, primary patency, secondary patency, as well as freedom from ipsilateral central neurologic event rate, re-operation, explant, and restenosis ($\geq 50\%$ stenosis). Kaplan-Meier plots for survival will include the following mortality classifications: all causes of mortality, vascular-related mortality and device-related mortality (as applicable). The remaining plots will be specific to indication, if the sample sizes allow for the creation of meaningful plots.

The incidence of adverse events will be categorized and summarized with percentages for the aggregate sample. Adverse events will be divided into early and late post-operative events to represent the distribution of occurrences. Events will be considered as early events if the event occurs <30 days after the operation, while late post-operative events will be considered to be all events happening after this time period. Early and late events will be presented by indication for surgery, seriousness of event, and relation to PhotoFix. Adverse events occurring secondary to

another complication will be collected, but not included in the calculation of adverse event rates. Adverse events occurring prior to PhotoFix implant will not be reported.

An interim analysis of the data will be performed approximately 6 months after the initiation of enrollment. The sample size will be dependent on enrollment rate; follow-up could range from 0 days to 5 months. This analysis will be used to assess the interim performance and safety of PhotoFix. The analysis of this data will also be used to address the planned enrollment of the study and to determine if any modifications to the study are necessary.

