Patient demographics and medical history, including medications, comorbidities, pertinent surgical history, and fundamental vascular diagnosis, will be collected at time of consent. Medications will only include drugs of interest and will not require a complete listing. Adverse events will be collected after surgery on all patients consented and enrolled into the study. The investigation will be conducted for a period necessary to collect all follow-up, as needed on each patient, but will not exceed 7 months after surgery. The total time a patient will be followed will be determined by their date of surgery; dates of surgery should occur within 60 days of consent. If the patient's surgery is scheduled after 60 days, a re-screen request must be submitted to the Sponsor. The anticipated final follow-up will be conducted in November 2019, but will ultimately be determined by IRB approvals, site activation, and by rate of patient enrollment.

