3.4.5 Intraoperative Evaluation

Patients that meet the study criteria will receive PhotoFix as a vascular patch, per the IFU. A patient will remain eligible for continuation if PhotoFix remains implanted at the conclusion of their vascular surgery; patients would be considered enrolled at this point. Peri-operative and post-operative (<24 hours after surgery) data will be collected on all enrolled patients; this data will be entered into the Operative Assessment eCRF (Appendix D). The following measures will be monitored and documented per indication, but may include:

- Surgery date
- Implanting surgeon
- Number of PhotoFix Patches Used
- PhotoFix lot number(s)
- PhotoFix patch size(s) (indicated on box(es))
- Patch implant site
- Surgical procedure description
- Concomitant procedure description
- Any adverse events, device malfunctions, or intraoperative mortality
- Peri-operative imaging data

Any intraoperative adverse events will be captured on the Adverse Event eCRF (Appendix D). Patients will be told to contact the investigator in the event of any complications which occur during the study. The contact information for the Principle Investigator is included in the copy of the signed ICF each consented patient will have received.

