## 2.9. Definition of Analyses

All analyses will focus on outcomes reported during the follow-up period, after PhotoFix implant. Analyses will summarize data collected through the end of follow-up; analyses at each time point are not planned, unless otherwise indicated.

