## **2.17. Adverse Events**

Adverse events will not be coded. The incidence of adverse events will be summarized for the aggregate sample. Adverse events will be considered as any event happening during or after PhotoFix implant. Any adverse event that occurs prior to surgery will not be included in the summary or analysis.

Adverse events will be summarized based on timing, in relation to surgery. Events will be categorized as early if the event occurs  $< 30$  days after surgery, while late post-operative events will be considered as events occurring  $\geq 30$  days after surgery.

Adverse events will be summarized by pre-specified category; events classified as other will be manually classified, as deemed appropriate. The following will be included in the summary of adverse events: consequence of event, required drug treatment or intervention, severity, relation to surgery, relation to PhotoFix, and status of event at end of study. Events deemed to be related to PhotoFix, with any definitive assessment, will be summarized in a frequency table; additional information discovered during event investigation will be described, as deemed necessary.

Adverse event rate will be presented as frequency counts and percentages in a table for enrolled patients. Adverse events will be presented in aggregate and by surgical indication.

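### Inconsistent starts for the event window could leave a neurologic event during endarterectomy, before patch placement, out of the CEA primary rate

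*Protocol*

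**What the plan says.** Several places set, or imply, when events begin to count.

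- Protocol 3.2: "Adverse events will be collected after surgery on all patients consented and enrolled into the study".
- Protocol 3.4.5: "Any intraoperative adverse events will be captured on the Adverse Event eCRF (Appendix D"). Footnote 3 to Table 2 agrees, allowing adverse event forms for the perioperative as well as the postoperative period.
- Protocol 6.7, closing the adverse event paragraphs: "Adverse events occurring prior to PhotoFix implant will not be reported".
- SAP 2.9, which heads both the primary and the secondary analyses: "All analyses will focus on outcomes reported during the follow-up period, after PhotoFix implant".
- SAP 2.17: "Adverse events will be considered as any event happening during or after PhotoFix implant", followed by "Any adverse event that occurs prior to surgery will not be included in the summary or analysis".

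The CEA endpoint is set in Protocol 6.1: "In the case of CEAs, the primary endpoint of the study will be rate of ipsilateral central neurologic events", with the components listed as "Ipsilateral central neurologic events: Transient ischemic attack, amaurosis fugax, stroke, and symptomatic carotid occlusion". Neither that section nor SAP 2.9.1 or 2.10 says when counting starts. SAP 2.10 tabulates the endpoint in enrolled patients who received the patch during CEA.

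**The concern.** These statements cannot all hold. They differ over one interval in particular: from the beginning of the operation to the moment the patch is in. That interval exists in every CEA in the study, because the patch closes a vessel that has already been prepared and opened; the photograph sequence in Protocol 3.4.4 shows the prepared vessel as a stage before implantation.

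The CEA endpoint counts neurologic events whatever their cause. Relation to the surgery and relation to the device are separate items on the Adverse Event eCRF, so a cut at implant is not needed to isolate device effects. If such a cut were applied, two analysts working from the same documents could report different primary rates, and the disagreement could only make the stricter reading's rate lower. The early adverse event rate (under 30 days) would be affected in the same way.

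**Working it through.** **1. One test case against each statement.** Take a CEA patient who has an ipsilateral stroke after skin incision and before patch placement, and whose patch is then implanted and stays in.

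| Place | Start implied | Treatment of this stroke |
|---|---|---|
| Protocol 3.2 | End of surgery | Not collected |
| Protocol 3.4.5; Table 2, footnote 3 | Perioperative period | Recorded |
| Protocol 6.7 | Implant | Not reported as an adverse event |
| SAP 2.9 | After implant | Outside the stated focus of all analyses |
| SAP 2.17, inclusion sentence | Implant | Outside |
| SAP 2.17, exclusion sentence | Surgery | Not excluded |
| Protocol 6.1; SAP 2.9.1 and 2.10 | None given | Undecided |

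**2. Denominator.** Protocol 3.4.5 treats the patient as enrolled once the operation ends with the patch in place. SAP 2.2 enrols everyone who receives it. SAP 2.10 therefore includes this patient, whether or not the stroke is counted.

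**3. Link to the primary data.** All four endpoint components are event categories on the Adverse Event eCRF (Appendix D, item 5). A rule for adverse events can therefore reach the primary endpoint, because the endpoint has no window of its own to override it.

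**4. Can the forms apply a cut at implant?** The Adverse Event eCRF records the start as month, day and year (item 3). The Operative Assessment eCRF separates only perioperative from postoperative (item 9). No structured field places an event on the day of surgery before or after implant. The cut would rest on narrative, source documents or judgement, and a deficit first seen when the patient wakes may have no observable onset.

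**5. Size.** The documents give no number of CEA patients and no expected event rate, so the following is illustration on assumed numbers. One omitted event lowers the rate by 1/n:

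- n = 30: 1/30 = 3.3 percentage points
- n = 50: 1/50 = 2.0 percentage points
- n = 70: 1/70 = 1.4 percentage points

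If that event were the only one among 50, the report would change from 1/50 = 2.0% (exact 95% CI 0.1 to 10.6) to 0/50 = 0% (0 to 7.1).

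**6. Planning figures.** The one derived figure, about 166 patients to consent, reproduces as 100 / (0.90 × 0.67) = 165.8 and does not depend on the window. SAP 2.20 gives no power calculation, so no error rate or power is affected.

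**The case against.** The strongest defence is that the exclusions are meant for the time between consent and surgery, which can run to 60 days. Protocol 3.2 contrasts baseline data taken at consent with events collected later, and the exclusion sentence in SAP 2.17 fits that purpose. The sentence in Protocol 6.7 sits with the adverse event summaries; the CEA endpoint has its own paragraph there, which says that every listed event will be summarised. SAP 2.9 speaks of a focus, which is scope wording rather than an exclusion rule. Intraoperative events are recorded, and SAP 2.1 and 2.21 promise listings of all data. With a date-only start, a stroke on the day of surgery carries the same date as the implant, so no structured field would remove it automatically.

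Most of this stands as a limit on the point. A reader might infer that the plan definitely excludes these strokes and so biases the primary rate downward; the wording does not go that far. A reader might also infer that comparability with published perioperative stroke rates is lost. Protocol 1.5 gives odds ratios and p-values, not such rates, and neither document plans a comparison. Nor is timing wholly unrecoverable: the event form has a free-text description, Protocol 4.3 asks for source documents, and full source verification is intended.

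The defence does not supply the missing start. The reference in Protocol 6.7 to all events is followed by a list of event types, not a time window. Protocol 4.1 gives an end to event reporting but no clear beginning. No passage says that intraoperative neurologic events count toward the CEA endpoint.

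**Conclusion.** The concern holds as an internal contradiction that should be fixed. The start of the event window is inconsistent across Protocol 3.2, 3.4.5 and 6.7 and SAP 2.9 and 2.17, and the CEA primary endpoint does not settle it. A strict reading of Protocol 6.7 and SAP 2.9 would let a neurologic event between the start of the operation and patch placement leave the numerator while the patient stays in the denominator. That could lower the reported rate; it is not certain to. The effect per event is the 1/n shown above and rests on an assumed CEA number. How often such events occur cannot be judged from the documents. The study is single-arm and descriptive, so the consequence is confined to the reported rates, but those rates are its main product.

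**What to change.** In Protocol 3.2 and 6.7 and SAP 2.9 and 2.17, state one start for the event window: the start of the index operation, defined as a single moment such as skin incision, for all enrolled patients who receive PhotoFix. Count every ipsilateral central neurologic event (CEA) and every adverse event otherwise eligible for the rates from that moment to the end of follow-up. Reword the Protocol 6.7 sentence so that it excludes only events before the start of the index operation. Setting the boundary at the day of surgery instead would leave same-day events before the operation unresolved.

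Events thought to precede patch placement may be listed descriptively, from the narrative or source documents, but should not be excluded.

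The cost is wording changes in both documents and a possibly slightly less favourable rate. One added field for timing relative to implant is optional, and would be needed only if that listing is to come from structured data.

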6.8 Privacy of Patient Data & Patient De-identification

All patient data will remain confidential. Patient names, social security number, addresses, or any other identifying information will not be reported. Patients and their data will be de-identified with the use of a Screening ID. Patients will sign a HIPAA waiver acknowledging that their information will remain confidential. The sample HIPAA waiver is attached in Appendix A.

The site will be provided with a patient log that they will use to record the Screening ID and patient information at the time of each screening. The site is responsible for maintaining the log. The unique 4-digit Screening ID will be assigned per the following scheme: the first two digits are the site assigned abbreviation, followed by the sequential number in which the patient was consented.

Example: The 1st patient screened at site CR

Site (2 letter)	Patient Enrolled (2 digit)
C	R

6.9 Record Maintenance

All correspondence related to this study should be kept in appropriate study files. Patient records, source documents, and IRB and Sponsor correspondence pertaining to the study must, be kept on file.

7 SITE MANAGEMENT PLAN AND MONITORING

It is the responsibility of CryoLife to ensure proper management of the clinical study. Frequency of site visits will be determined by any of the following criteria: patient volume at a site, site compliance with the study protocol, and study duration. Site visits may be completed in person or remotely. One hundred percent source document verification (SDV) is intended for this study. Exceptions to this monitoring goal will include screen failures. One hundred percent SDV for screen failures will be restricted to the following eCRFs: Informed Consent, Eligibility Evaluation, and Demographics.

Study management will be performed by appropriately trained personnel appointed by the Sponsor and will be documented per standard operating procedures (SOPs) to ensure that the clinical study is conducted in accordance with:

- The signed Investigator Agreements
- The protocol
- Food and Drug Administration (FDA) regulations (as applicable) and Good Clinical Practice (GCP)

